9.2 Analysis Sets

For the purposes of analysis, the subject analysis sets are defined in [Table 12](#).

Table 12: Subject Analysis Sets

Analysis Set	Description
All Enrolled Subjects	All participants who sign the informed consent form and receive approval from the sponsor to be enrolled and treated.
Safety Analysis Set	All participants enrolled in the study who receive any amount of ZW25, palbociclib, and/or fulvestrant.
DLT Evaluable Set	All subjects who receive $\geq 75\%$ of the planned total dose of each component of study treatment (ZW25, palbociclib, and fulvestrant) over the first 28 days of treatment, and are followed for the full DLT evaluation period, unless the reason for not receiving required doses or not being followed is the occurrence of DLT.
mITT Set	All subjects in the safety analysis set who had at least one identifiable (target and/or non-target) lesion at baseline and at least one post-baseline disease assessment or discontinued all study treatment and are no longer being followed for efficacy.
Measurable Disease	All subjects in the safety analysis set who had at least one measurable target lesion at baseline and at least one post-baseline disease assessment or discontinued the study due to death, clinical or radiologic progressive disease, or an AE.
Pharmacokinetics	All subjects in the safety analysis set who have sufficient post-dose samples collected to allow estimation of the PK. Subjects who have protocol deviations that could affect the PK evaluation, will be noted and may be excluded from the PK analysis set depending on the type of the deviation.

AE= adverse event; DLT = dose-limiting toxicity; mITT = modified intent to treat; PK= pharmacokinetics

9.3 Statistical and Analytical Plans

The statistical analysis plan (SAP) will be developed and finalized before database lock and will provide additional details regarding the statistical methods, endpoints, and analyses to be performed as well as the procedures for accounting for missing, unused, and spurious data, and deviations from the statistical analysis methods described in the protocol. This section is a summary of the planned statistical analyses of the primary, secondary, and exploratory endpoints. Any changes to the methods described in the final SAP will be described and justified in the clinical study report.

9.3.1 General Considerations

The primary efficacy analyses will be conducted after all subjects in Part 2 have either reached a progression-free survival time of at least 6 months or are considered to have a progression-free survival event (disease progression per RECIST v1.1, clinical progression or death) prior to 6 months, or are permanently censored for progression-free survival prior to 6 months. The final efficacy analyses will be conducted after all subjects have completed their treatment and the follow-up period or following study termination by the sponsor

9.3.1.1 Randomization and Blinding

This is an open-label, non-randomized study. Randomization and blinding will not be performed. Subjects will be assigned to each cohort sequentially.

9.3.1.2 Adjustments for Covariates

No adjustments for covariates will be performed.

9.3.1.3 Handling of Dropouts and Missing Data

Methods for handling of missing, unused, or spurious data will be detailed in the SAP.

9.3.1.4 Multicenter Studies

No comparisons between sites will be performed.

9.3.1.5 Multiple Comparisons and Multiplicity

No adjustments for multiple comparisons will be performed.

9.3.1.6 Data Transformations and Derivations

Data transformations, conventions, and derivations will be detailed in the SAP.

9.3.1.7 Examination of Subgroups

Potential subgroups to be evaluated and their associated analyses will be detailed in the SAP.

9.3.2 Subject Disposition

An accounting of study subjects by disposition will be tabulated and the number of subjects in each analysis set will be summarized. Subjects who discontinue study treatment and subjects who withdraw from the study will be summarized with reason for discontinuation or withdrawal.

9.3.3 Subject Characteristics

Baseline demographics and disease characteristics will be summarized using counts and percentages for categorical variables and summary statistics (e.g., mean, quartiles, standard deviation, and range) for continuous variables.

9.3.4 Treatment Compliance

The dose administered at each cycle for each treatment agent will be assessed and dose intensity will be summarized. Details will be provided in the SAP.

9.3.5 Efficacy Analyses

All efficacy analyses will be conducted on the Safety analysis set unless otherwise specified. Efficacy for Part 1 of the study will be summarized descriptively by dose cohort. For Part 2 of the study, subjects treated at the RD in Part 1 will be included in the analyses of efficacy.

9.3.5.1 Progression-free Survival (PFS)

Progression-free survival (PFS) time is defined as the time from first dose of ZW25, palbociclib, and/or fulvestrant to the date of first documented disease progression (per RECIST 1.1) or death from any cause, whichever occurs first. Subjects who are alive and have not progressed at the time of the analysis will be censored at the time of their last evaluable tumor assessment. Subjects who have received subsequent anticancer therapy excluding radiotherapy without a prior reported progression will be censored at the time of their last evaluable tumor assessment on or prior to the initiation of first subsequent anticancer therapy. Details of the censoring scheme for this analysis will be described in the SAP.

Kaplan-Meier plots and estimates of the quartiles and their corresponding 95% confidence intervals will be computed.

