Part 2 of the study will evaluate the preliminary anti-tumor activity using the modified intent to treat (mITT) set. The mITT set includes all subjects who receive any amount of ZW25 with palbociclib and/or fulvestrant who had at least one identifiable (target and/or non-target) lesion at baseline and at least one post-baseline disease assessment or discontinued all study treatment and are no longer being followed for efficacy. All subjects will be assessed for safety and anti-tumor response. The primary efficacy endpoint will be PFS6 (defined as the % of mITT subjects with PFS of ≥ 24 weeks); secondary efficacy endpoints include ORR, DOR, DCR, PFS, and OS. Approximately 50 subjects are expected to be enrolled in Part 2.

If possible, an additional optional tumor biopsy may be obtained at the time of disease progression from an accessible site to allow for assessment of changes in HER2 expression as well as the presence of other exploratory biomarkers. Biomarkers of response may be evaluated.

Test Product, Dose, and Mode of Administration

Note that ketoconazole and other strong CYP3A4 inducers and inhibitors are prohibited.

ZW25 (investigational agent):

- Part 1:
 - 20 mg/kg IV ZW25 Q2W on Days 1 and 15 of each 28-day cycle. A step-down dose level to 15 mg/kg Q2W or another dose level (not lower than 15 mg/kg) of ZW25 may be evaluated if recommended by the SMC and approved by the sponsor
- Part 2:
 - RD of ZW25 as confirmed in Part 1 of the study

Combination Products (Dose and Mode of Administration)

Palbociclib (capsules for oral use):

- Parts 1 and 2:
 - 125 mg PO QD for the first 21 days of each 28-day cycle. Step-down dose levels of 100 and/or 75 mg PO QD may be evaluated if recommended by the SMC and approved by the sponsor.

Fulvestrant (injection for IM administration):

- Parts 1 and 2:
 - 500 mg IM Q2W for 3 doses (Cycle 1 Days 1 and 15 and Cycle 2 Day 1), and Q4W thereafter

LHRH analogue:

- Parts 1 and 2: Per institutional guidelines.

Note: Concomitant norethindrone acetate is contraindicated for breast cancer patients.

Required Premedications:

- Required concomitant premedication for potential infusion reactions:
 - Prior to each ZW25 infusion:
 - Acetaminophen orally (650 mg) and diphenhydramine orally (50 mg) or equivalents of each; approximately 30 to 60 minutes prior to infusion of ZW25
 - Corticosteroids (hydrocortisone 100 mg IV or dexamethasone 10 mg IV); approximately 30 to 60 minutes prior to infusion of ZW25

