week) later. Following progression or start of subsequent anticancer therapy, disease assessments will be discontinued and subjects will enter long-term follow-up for survival status. Data on survival will be collected via clinic visits (if feasible) or via telephone calls every 3 months after the last follow-up visit. Subjects may be discontinued from the study due to death, lost to follow-up, consent withdrawal or study termination by sponsor. Reason for study discontinuation will be recorded. The same assessment schedule ([Appendix A](#)) will be used for subjects in both parts of the study. All subjects in Part 1 will have blood samples taken per the extensive sampling schedule ([Appendix B](#)). In Part 2, at least 6 subjects will have blood samples taken per the extensive sampling schedule ([Appendix B](#)) while the remaining subjects will have samples taken based on the sparse sampling schedule ([Appendix C](#)).

Figure 2: Overall Study Design

CT = computed tomography; D = day; MRI = magnetic resonance imaging; Q8W = every 8 weeks.

Note: On Days 1 and 15 of each cycle, ZW25 will be administered first followed by palbociclib and fulvestrant.

Note: The DLT-evaluation period will be the initial 28 days of treatment beginning Cycle 1 Day 1.

*, Subjects who discontinue treatment with all 3 drugs for any reason (except death or withdrawal of consent) on either part of the study will have an end-of-treatment (EOT) visit within 14 days after the last dose of study drug and safety follow-up visit at approximately 30 days after the last dose of study drug.

**, Subjects who discontinue all study treatment for reasons other than progressive disease or start of subsequent anticancer therapy will continue in follow-up with disease assessments approximately every 8 weeks after the previous scan until disease progression or start of subsequent anticancer therapy.

***, Following progression or start of subsequent anticancer therapy, disease assessments will be discontinued and subjects will enter long-term follow-up for survival status. Data on survival will be collected approximately every 3 months after the last follow-up visit.

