5.2.7.3 Prohibited Concomitant Therapy

Subjects may not receive cancer related surgery, radiotherapy (except as noted in [Section 5.2.7.2](#) above), other investigational, or systemic anti-neoplastic therapy during the study. Use of alternative supplemental therapies is discouraged and use of any such product must be recorded.

Ketoconazole and other strong CYP3A4 inducers and inhibitors (see also [Section 5.3.6](#)) are prohibited during the study.

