5.4 Duration of Study Treatment

In both parts of the study, subjects may continue on study treatment until radiographically-confirmed disease progression as defined by RECIST version 1.1, clinical disease progression, unacceptable toxicity, consent withdrawal, physician decision, pregnancy, protocol violation, start of a subsequent anticancer therapy, or study termination by the sponsor.

Note: Trastuzumab, alternate CDK4/6 inhibitors, or any other treatment not part of the study regimen will be considered subsequent anticancer therapy. Palliative radiotherapy to a non-target bone lesion that is not progressing is allowed after the second cycle of treatment and must be administered after the initial response assessment obtained per protocol. This will not be considered subsequent anticancer therapy but must not interfere with the assessment of tumor target lesions. Treatment with palbociclib should be interrupted during palliative radiotherapy.

If any component(s) of the combination therapy is discontinued due to toxicity deemed related to the component(s), subjects on either part of the study may continue to receive the other component(s) of the study regimen until disease progression or start of subsequent anticancer therapy. Subjects who discontinue treatment with all 3 drugs for any reason (except death or withdrawal of consent) on either part of the study will have an end-of-treatment (EOT) visit within 14 days after the last dose of study drug (ZW25, palbociclib, and/or fulvestrant) and safety follow-up visit at approximately 30 days after the last dose of study drug.

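### The PFS censoring rule disregards all radiotherapy, while the protocol exempts only one palliative type, so a subject given other radiotherapy before Week 24 can count as a PFS6 success

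*Combined protocol and SAP*

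**What the plan says.** **Analysis sections.** Section 9.3.5.1 states: "Subjects who have received subsequent anticancer therapy excluding radiotherapy without a prior reported progression will be censored". The censoring date is the last evaluable tumor assessment on or before the new therapy. The radiotherapy exclusion has no limit on site, intent or state of the lesion. For everyone else, "Subjects who are alive and have not progressed at the time of the analysis will be censored", again at the last evaluable assessment. The PFS events in Sections 9.3.5.1 and 9.3.5.2 are RECIST 1.1 progression and death from any cause. PFS6, the primary endpoint of Part 2, is the percentage of subjects whose PFS time is at least 24 weeks, with an exact binomial 95% interval.

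**Conduct sections.** Section 5.4 says that "any other treatment not part of the study regimen will be considered subsequent anticancer therapy". It makes one exception: "Palliative radiotherapy to a non-target bone lesion that is not progressing is allowed after the second cycle of treatment", provided the initial response assessment has been done. Of that case it says: "This will not be considered subsequent anticancer therapy but must not interfere with the assessment of tumor target lesions". Sections 3.1 and 4.4.1 carry the same note, and Section 5.2.7.2 repeats the exception. Section 5.2.7.3 prohibits the rest: "Subjects may not receive cancer related surgery, radiotherapy" and other anticancer treatment, apart from the exempt type.

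**Follow-up.** Sections 3.1 and 6.7 say: "Following progression or start of subsequent anticancer therapy, disease assessments will be discontinued", with survival follow-up only from then on. Section 6.5, however, schedules a visit about 30 days after the last dose for all subjects. It includes a scan unless one was done at the end-of-treatment visit or within the previous 4 weeks.

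**The concern.** The protocol defines subsequent anticancer therapy with care and leaves one narrow kind of radiotherapy outside it. The PFS rule then sets that definition aside and disregards radiotherapy altogether. Radiotherapy to a target lesion, a progressing lesion or the brain is thus subsequent therapy for trial conduct but not for PFS censoring.

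The case is foreseeable. Under Appendix D bone lesions are non-measurable, and non-target progression must reflect a change in overall disease status, not growth of one lesion. A single growing bone lesion could be irradiated with no RECIST progression on record, and that radiotherapy is not exempt because the lesion is progressing. Subjects with stable, treated brain metastases are eligible, so later brain radiotherapy is also possible.

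At stake is the primary endpoint of an uncontrolled study with investigator-assessed progression. A subject who starts systemic therapy before Week 24 without progression is censored at the last earlier scan. One who starts non-exempt radiotherapy in the same circumstances is not, and the protocol gives no reason for the difference.

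**Working it through.** **1. The plan's own figures.** Table 11 gives exact 95% intervals at N=50. Clopper-Pearson limits are the beta quantiles B(0.025; x, n−x+1) and B(0.975; x+1, n−x). They give 20/50: 26.41–54.82%; 25/50: 35.53–64.47%; 30/50: 45.18–73.59%; 35/50: 55.39–82.14%. All four round to the stated values. The mismatch leaves this table intact; it affects who is counted as a success.

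**2. Following one subject through the rules.** Suppose the Week 8 scan shows no progression and non-exempt radiotherapy starts at Week 10. The timings are illustrative.

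| What happens next | Current 9.3.5.1 | Exclusion limited to exempt radiotherapy |
|---|---|---|
| Alive, no further scans | Censored Week 8; PFS6 not achieved | Same |
| No progression recorded; death at Week 40 | Event at Week 40; PFS6 achieved | Censored Week 8; not achieved |
| Scans continue past Week 24, no progression | PFS at least 24 weeks; PFS6 achieved | Censored Week 8; not achieved |
| RECIST progression at Week 16 | Event at Week 16; not achieved | Censored Week 8; not achieved |

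PFS6 is a simple proportion, so a subject censored before 24 weeks counts as not achieving it.

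**3. Is a scan due after Week 8?** Take the last dose as near Week 10. The safety visit falls at about 10 + 30/7 = 14.3 weeks, which is 6.3 weeks after the Week 8 scan. That exceeds 4 weeks, so Section 6.5 calls for a scan unless one was done at end of treatment. Section 6.7 points the other way. If the scan is done and shows progression, the event is near Week 14 and PFS6 is not achieved. If it shows none, or is not done, the second row of the table stands.

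**4. Direction.** The narrower exclusion can only shorten a subject's PFS time or leave it unchanged, because it censors on or before the radiotherapy. PFS6 can therefore only fall or stay the same. Kaplan-Meier PFS can move either way: the fourth row loses an early event, while the second loses long event-free time that was not supported by scans.

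**5. Size.** One subject is 1/50 = 2.0 points. If six Part 1 subjects at the recommended dose are added under Section 9.3.5, N = 56 and one subject is 1/56 = 1.8 points. The documents give no count of affected subjects, so k = 1 to 3 is an assumption. Starting from an observed 25/50 (50%; 35.5–64.5%) that contains k false successes:

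- k = 1: 24/50 = 48% (33.7–62.6%)
- k = 2: 23/50 = 46% (31.8–60.7%)
- k = 3: 22/50 = 44% (30.0–58.7%)

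**The case against.** The strongest reply is that the exposure is narrow. The radiotherapy at issue is prohibited, so the gap needs a protocol departure, no earlier RECIST progression, and then a death at or after Week 24 or continued scans without progression. End-of-treatment evaluations must precede new therapy, and sites are asked to make every effort to confirm progression radiographically. The death route also arises because Section 9.3.5.1 has no missed-assessment rule, a weakness that is not specific to radiotherapy. All of this stands, and it limits the likely number of subjects.

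Second, following subjects through radiotherapy is a defensible choice, and censoring those irradiated for worsening disease may be informative. That is a real cost of the fix. It does not defend the current combination, because a policy of disregarding radiotherapy needs scans to continue afterwards and the protocol stops them.

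Third, Section 9.3.5.1 leaves censoring details to the SAP, and the document reviewed contains no SAP censoring table. The SAP might narrow the term or add a missed-scan rule. The Amendment 4 history says the section was revised to agree with the SAP, so the SAP may equally carry the same wording. Either way, the rule stated in the protocol needs correcting.

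A reader might infer three stronger things that the documents do not support:

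- **That Kaplan-Meier PFS is also biased favourably.** The Week 16 case shows that the current rule keeps an event which censoring would remove.
- **That these subjects have no scan after radiotherapy.** Section 6.5 may still require one.
- **That the censoring rule inflates the disease control rate.** Section 9.3.5.4 defines that rate from best response, and it does not depend on Section 9.3.5.1.

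**Conclusion.** The inconsistency is in the current text and should be corrected. Followed as written, Section 9.3.5.1 lets a subject with non-exempt radiotherapy before Week 24 and no reported RECIST progression count as a PFS6 success by either of the two routes shown. For those subjects the error is favourable on PFS6, by 2.0 points each at N=50. The effect on Kaplan-Meier PFS has no established direction.

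The likely total is small. One to three subjects, an assumed range, would mean 2 to 6 points, against a planned interval of 36% to 64% at an observed 50%. The plan sets no success threshold for PFS6, so no formal decision would change.

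A neighbouring conflict remains. Section 9.3.1 lists clinical progression as a PFS event, but Section 9.3.5.1 does not. How a subject irradiated for clinical worsening is classified depends partly on settling that as well.

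**What to change.** In Section 9.3.5.1 and the SAP censoring table, replace *excluding radiotherapy* with *excluding palliative radiotherapy permitted under Section 5.2.7.2*. Any other radiotherapy before progression then censors PFS at the last evaluable assessment on or before its start. State that the subject counts as not achieving PFS6 if that assessment falls before 24 weeks.

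Add a sensitivity analysis of PFS that keeps later progressions and deaths in these subjects, and report how many there are.

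The cost is one phrase, one table row and one extra analysis. PFS6 may come out slightly less favourable. The main Kaplan-Meier analysis loses later events in these subjects, possibly through informative censoring, which is why the sensitivity analysis is needed. Applying the rule also requires the date and site of radiotherapy and the status of the lesion; the documents do not show whether the case report form records these. No clinical rule changes.

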9.3.5.2 Progression-Free Survival at 6 Months (PFS6)

Progression-free survival at 6 months (PFS6) is defined as having a progression-free survival time ³ 24 weeks at the time of analysis where PFS time is defined as the time from the first dose of ZW25, palbociclib, and/or fulvestrant to the date of documented disease progression (per RECIST 1.1) or death from any cause. The percentage of subjects achieving PFS6 and the corresponding exact binomial 95% confidence interval (CI) will be calculated.

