6.7 Survival Follow-Up (Every 3 Months)

Following progression or start of subsequent anticancer therapy, disease assessments will be discontinued, and subjects will enter long-term follow-up for survival status. Data on survival will be collected via clinic visits (if feasible) or via telephone calls every 3 months after the last follow-up visit. Subjects may be discontinued from the study due to death, lost to follow-up, consent withdrawal or study termination by sponsor. Reason for study discontinuation will be recorded.

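### PFS6 credits a death, or progression first found, after Week 24 however early the last scan was, while the same subject alive and unscanned is not credited

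*Combined protocol and SAP*

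**What the plan says.** **Endpoint.** Section 2.2 makes PFS6 the only primary endpoint of Part 2. Under 9.3.5.2 it "is defined as having a progression-free survival time ³ 24 weeks at the time of analysis" (the stray character is a misread at-least sign; Section 2.2 shows it correctly). PFS time there runs "to the date of documented disease progression (per RECIST 1.1) or death from any cause". The estimate is a simple proportion with an exact binomial 95% interval.

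**Censoring.** Under 9.3.5.1, subjects "alive and have not progressed at the time of the analysis will be censored at the time of their last evaluable tumor assessment". Those who start another anticancer therapy without prior progression "will be censored at the time of their last evaluable tumor assessment on or prior to the initiation of first subsequent anticancer therapy". The section adds: "Details of the censoring scheme for this analysis will be described in the SAP". The supplied document contains no separate SAP text with such a scheme.

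**Timing.** Section 9.3.1 sets the primary analysis for when every Part 2 subject has reached 6 months, has had a PFS event, or belongs to those who "are permanently censored for progression-free survival prior to 6 months". Its list of PFS events includes clinical progression. The definitions in 9.3.5.1 and 9.3.5.2 do not.

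**Scans.** Scans are due every 8 weeks, ±7 days (Appendix A, footnote e). Subjects who stop all treatment for reasons other than progression or new therapy stay on 8-weekly scans (Section 6.6). If they stop before Week 24 they must have a Week-24 assessment, waived when the last one was no more than 4 weeks earlier (Section 3.1; Appendix A, footnote v). Once progression or new therapy has occurred, "disease assessments will be discontinued, and subjects will enter long-term follow-up for survival status" (Section 6.7).

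**The concern.** A subject should count as progression-free at 24 weeks because a scan at about that time, or later, showed no progression. The rule as written also accepts a late event as proof. When the last scan was well before Week 24, a death or a progression detected only after Week 24 says little about tumour status at Week 24, yet it lengthens PFS time past the threshold. The same subject, still alive with no further scan, stays censored at the early scan and falls short.

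The error runs one way: it can only raise PFS6. It can also grow with follow-up, because deaths continue to be recorded every 3 months. A subject who was not a success at the primary analysis could become one at the final analysis with no new tumour information. Part 2 has a single arm, so no comparator shares the bias.

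**Working it through.** **1. The plan's own figures.** Exact 95% limits for x of n are the 0.025 quantile of Beta(x, n−x+1) and the 0.975 quantile of Beta(x+1, n−x). For 20, 25, 30 and 35 of 50 they are 26.4–54.8%, 35.5–64.5%, 45.2–73.6% and 55.4–82.1%. Table 11 reproduces.

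**2. The rules applied to example subjects.** PFS time is the first of RECIST progression or death. If there is neither, or if new therapy came first, it is the last evaluable scan. Success is a PFS time of at least 24 weeks.

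| Last clear scan | Then | PFS time (weeks) | PFS6 |
|---|---|---|---|
| Week 8 | alive, no further scan | 8, censored | no |
| Week 8 | dies Week 30 | 30, event | yes |
| Week 8 | progression first found Week 32 | 32, event | yes |
| Week 16 | alive, no further scan | 16, censored | no |
| Week 16 | dies Week 26 | 26, event | yes |
| Week 16 | dies Week 20 | 20, event | no |
| Week 16 | new therapy Week 18, dies Week 30 | 16, censored | no |
| Week 23 (in window) | alive, no further scan | 23, censored | no |

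Rows 1 to 3 show the defect. The new-therapy row shows its limit. The last row shows a related problem: an on-time Week-24 scan done up to 7 days early does not by itself reach 24 weeks.

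No sentence says how subjects censored before Week 24 are classed. That they are not successes follows from the 9.3.5.1 censoring date combined with a simple proportion.

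**3. Who can be affected.** Subjects without new therapy who miss or refuse scans are one group. The other is those stopped for clinical progression without RECIST progression. Section 4.4.1 treats clinical progression as progressive disease, so the off-treatment scans and the Week-24 assessment, which are for subjects stopping for other reasons, need not reach them. The end-of-treatment scan is waived if one was done within 4 weeks (Section 6.4).

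**4. Size per subject.** At N=50 each such subject adds 1/50 = 2 points. From 20/50 = 40% (26.4–54.8), one gives 42% (28.2–56.8) and three give 46% (31.8–60.7).

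**5. Size under assumed dropout.** The documents give no dropout or post-dropout survival figures, so these inputs are assumptions. A share d leaves imaging before Week 24 without RECIST progression, at a time U uniform on Weeks 4–20, and survival afterwards is exponential with median m. With λ = ln 2/m, the shift at analysis week A is

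d × E[exp(λU)] × (exp(−24λ) − exp(−Aλ)), where E[exp(λU)] = (exp(20λ) − exp(4λ))/(16λ).

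Central case, d = 10% and m = 40 weeks: λ = 0.01733 and E[exp(λU)] = (1.4142 − 1.0718)/0.2773 = 1.235.

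- A = 40: 0.10 × 1.235 × (0.6598 − 0.5000) = 2.0 points.
- A = 60: 0.10 × 1.235 × (0.6598 − 0.3536) = 3.8 points.

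These agree with a simulation of 400,000 draws. Over d = 6–14% and m = 26–60 weeks the ranges are 0.9–3.6 points (A = 40) and 1.8–6.3 points (A = 60).

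**6. Why these are upper-type figures.** The model counts every death from Week 24 to analysis among all who leave imaging. It ignores new-therapy censoring and consent withdrawal. If 50–80% of leavers fall in those groups (assumption), multiplying by 0.5 to 0.2 gives 1.0 to 0.4 points at Week 40 and 1.9 to 0.8 at Week 60.

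**The case against.** **The protocol protects the endpoint.** Off-treatment subjects stay on scans and must have a Week-24 assessment, and sites are asked to confirm progression radiographically. This stands as a limit on frequency. None of it is part of the endpoint definition, so a subject who misses the scan is still classed as in the table.

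**The SAP may hold a missed-assessment rule.** Section 9.3.5.1 leaves censoring detail to it, and 9.3.1.3 leaves missing data to it. That could close the gap. But no such rule is in the supplied text, and the Amendment 4 log says 9.3.5.1 and 9.3.5.2 were revised to match the SAP.

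**Three stronger readings are tempting, and the documents do not support them.**

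- A reader might infer that someone who starts another drug at Week 10 and dies at Week 30 is a success, because 9.3.5.2 does not repeat the new-therapy rule. But the living subject is a non-success only if the 9.3.5.1 censoring governs PFS6. If it does, the new-therapy sentence beside it governs too and that subject is censored.
- A reader might infer from Section 6.7 that any early stop leads to survival follow-up alone. That follow-up starts only after progression or new therapy.
- A reader might infer that success never needs a scan around Week 24. A living, event-free subject does need one at or after Week 24. Success without one comes only through death or late-found progression.

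**Nothing hangs on the number.** Part 2 has no hypothesis, threshold or go/no-go rule, and one or two subjects are small against an interval of about ±14 points. This stands, and it sets the severity.

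**Conclusion.** The defect is real but narrow. Read together, 9.3.5.1 and 9.3.5.2 class a subject as progression-free at 24 weeks because of a later death or late-found progression, whatever the gap since the last scan, and do not so class the same subject alive and unscanned. It applies to subjects without new anticancer therapy who miss or refuse scans, or whose scans stop after clinical progression without RECIST progression. On that second group the plan also contradicts itself: clinical progression is a PFS event in 9.3.1 and not in the two definitions.

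The size is 2 points per affected subject at N=50. How many there will be cannot be read from the documents. The central figures of 2.0 and 3.8 points rest on assumed dropout and survival and lean high. The mechanism is the same whether the mITT set (Section 2.2) or the Safety set (Section 9.3.5) is the denominator.

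A reader might call this a must-fix, since it touches the only Part 2 primary endpoint. The current plan does not support that: the analysis is descriptive and no stated decision would change. It is a should-fix.

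**What to change.** In 9.3.5.2, and in the same words in the SAP:

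1. State that the 9.3.5.1 censoring rules, including new-therapy censoring, apply to PFS6.
2. State that success requires an evaluable scan without progression at the scheduled Week-24 assessment (within its ±7-day window) or later. Where Appendix A, footnote v, waives the Week-24 follow-up scan, the scan within the preceding 4 weeks serves instead. There must be no progression, death or subsequent anticancer therapy before the qualifying scan or, if that scan precedes Week 24, before Week 24.
3. State that death, or progression first documented, after a Week-24 assessment was missed without such a scan is not a success.
4. Reconcile whether clinical progression is a PFS event across 9.3.1, 9.3.5.1 and 9.3.5.2.

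The waiver clause is needed. Without it, a compliant subject with a clear scan at Week 21, a validly waived Week-24 scan and progression first found at Week 29 would lose a success. The text must also say outright that an in-window Week-23 scan, or a validly waived earlier one, counts toward 24 weeks, because this departs from a literal PFS time of 24 weeks.

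The cost is a few sentences and no new data. Reported PFS6 may be slightly lower.
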